Table 2. Roles and Responsibilities.....	19
14. Documentation Checklist.....	19
15. Reference List	19
16. Appendices.....	19

1. Study Synopsis

Study Information	
Study Type	Retrospective chart review
Study Device(s)	Profound Matrix System is a platform of 3 applicators: Sublime, Sublative RF and Matrix Pro. The Matrix Pro applicator, a new short pulse RF micro-needling device that treats with an array of RF micro-needles penetrating the skin, will be assessed in this retrospective analysis.
Indication(s)	Wrinkles
Treatment area(s)	Full face
Overall Study Objective	Evaluate the safety and efficacy of the Profound Matrix System with the Matrix Pro applicator for treatment of wrinkles
Target Enrollment	This is a retrospective chart review evaluating all subjects enrolled into the FUFT2002 source study meeting inclusion criteria and none of the exclusion criteria of this study protocol for retrospective analysis.
Study duration	N/A – this is a retrospective chart review
Study Site(s)	In the source study from which data for the current retrospective study will be extracted, subject enrollment occurred at up to five (5) clinical sites.
Study Design	This study is a retrospective analysis of de-identified subject data collected during implementation of the clinical study, “Functional Usability and Feasibility Testing of the Profound Matrix™ System (FUFT2002)” (source study). The FUFT2002 clinical study was a multi-site prospective clinical trial. The current retrospective study will analysis data extracted from the FUFT2002 database according to prespecified study selection criteria.
List of Measures	
 • Before and after photograph assessment • Subject satisfaction questionnaire • Pain/ discomfort during treatment using Numerical Rating Scale (NRS) • Adverse events evaluation
Primary Efficacy Endpoint(s)	The Primary Efficacy Endpoint is pre-defined as the percentage correct before and after photograph determinations made by blinded evaluators based on perception of facial wrinkles.

[figure not shown]

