Safety Variables:	
 NA, Explain rationale:
 
Statistical hypotheses for safety variables are not applicable as formal safety evaluation is not required for this non-significant risk (NSR) retrospective study. As such, statistical significance evaluation of outcome is limited to the primary efficacy variable only, as explained above.

SAMPLE SIZE

Calculating Sample Size

Table 6

Sample Size Justification	
Clinical Background:	
The parameters used for sample size calculation were determined from that employed in prior pivotal clinical trials whose outcome data was used to successfully support an FDA 510(k) clearance for a comparable indication to that being evaluated in this study.

Expected Outcomes:	
As this is a retrospective, single arm study, minimally clinically meaningful difference between treatment groups is not applicable.
 
Expected outcome is that within the single arm active treatment group, the pre-determined primary success criteria of at least 2 of the 3 blinded evaluators correctly identifying the Before-After photo order for a minimum of 70% of subjects, will be met.

Estimated Retention	
N/A – This is a retrospective clinical study

Effect Size	
 N/A, Explain rationale:
 
There is no comparator arm.

Significance Level and Power Justification:	
Significance Level: $\alpha = 0.05$
 
Power: 80%
 
Type of t-test: Responder Rate Analysis: percent of successes.
 
 N/A, Explain rationale: N/A

	Name: MXP23001 Statistical Analysis Plan	
Number: 10-040-02025	Effective Date: See Agile	Revision: A

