Sample Size Calculation and Justification	
Employing these parameters, the minimum pre-determined sample size to provide sufficient power for a statistical comparison of the proportion of treatment responders (P) versus a reasonable cutoff (P0) is based on a power calculation utilizing the (one proportion) binomial exact test and based on the following assumptions.
 

 
Therefore, a sample size of 24 study subjects is determined to be sufficient to provide appropriate sample population for statistical analysis such that the results of this retrospective study can be considered statistically and clinically meaningful and generalizable to the broader intended population.
 
 N/A, Explain rationale: N/A

Target Number of Subjects per Site	A sample size of 24 study subjects has been determined sufficient to provide an appropriate sample population for statistical analysis and generalizability of results.

GENERAL ANALYSIS CONSIDERATIONS

Timing of Analyses

- The final analysis for primary efficacy will be performed after all qualified subjects from the source study have been identified per the retrospective study inclusion and exclusion criteria and enrolled in the retrospective study, after the final data entry has been entered into the current study database, and after each of the three independent blinded evaluators have completed their Before-After blinded photographic assessments.
- The final analysis will be performed on data recorded in the electronic Excel database, having been documented as meeting the cleaning and approval requirements of SOP 10-030-01617 (Global Clinical Data Management Procedure) and after the finalization and approval of this SAP document.

Analysis Populations

Table 7

Study Design and Plan	
Full Analysis Population/ Intention to Treat Population (or Modified Intention to Treat Population):	The Full Analysis Population in this retrospective study will be the per protocol population including all enrolled subjects who had valid recorded baseline and study endpoint outcomes recorded during the source study, including evaluable photographs at both assessments. The Full Analysis Per Protocol population analysis will be the primary and only analysis population in this retrospective study.

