 CANDELA™ Science. Results. Trust.	Name: MXP23001 Statistical Analysis Plan	
Number: 10-040-02025	Effective Date: See Agile	Revision: A

Adverse Events

The incidence rates and percentages of adverse events will be calculated with respect to each of number of subjects and number of treatment administrations. Wherein subject is the denominator, each subject will only be counted once, and any repetitions of adverse events will be ignored. All adverse events will be included in the summary and analysis.

SUBJECT SATISFACTION QUESTIONNAIRE

QUALITY ASSURANCE OF STATISTICAL ANALYSIS

Study data extracted from the source study database will be recorded on paper CRFs and then entered in the study database. Photographs will be stored electronically. Other source documentation (i.e., evaluations performed post-hoc from the photographs by the independent blinded evaluators) will be entered into the database at completion. Verification of the entry of the paper source documentation into the database will occur after the final entry has been made. Subsequently, the fully verified database will be locked. The database will be constructed using Microsoft Office Excel (Microsoft, Redmond, WA). The final dataset will be forwarded to an independent contracted biostatistician for analysis per the protocol Statistical Analysis Plan using SAS Version 9.4 or equivalent, as per the time of writing.

ROLES AND RESPONSIBILITIES OF SAP

Table 9

Roles and Responsibilities	
Name/ Title	Function
[name], B.S., M.S., AEMT – Independent Clinical Consultant/Biostatistician	Provide statistics for sample size calculation and input to data analysis plan and the final analysis.
[name] – Clinical Affairs Manager	Oversee study related procedures
[name] [name] – Senior Clinical Research Associate and Data Lead	
 • Oversee data monitoring and management. will review the data or analyses and make decisions. • what changes if any will be made to the study protocol, device, etc.
[name], [name], and [name] . – Clinical Research Associates	Oversee study related procedures, site monitoring, and collection of data
Principal Investigator(s) of Clinical Trial Sites	Ensuring that the source clinical study is conducted according to the investigational plan, and applicable FDA regulations. Protecting the rights, safety, and welfare of study subjects.

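### The 24 subjects were sized on the responder rate alone, so they do not support unqualified statements that the study's results are meaningful and generalizable; adverse-event rates need a measure of precision

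*SAP*

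**What the plan says.** The study objective, in the Protocol synopsis and SAP Table 2, is to "Evaluate the safety and efficacy of the Profound Matrix System with the Matrix Pro applicator for treatment of wrinkles".

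The only visible basis for the sample size is a power calculation that compares the responder proportion with a cutoff, "utilizing the (one proportion) binomial exact test" (Protocol section 11; SAP Table 6), at alpha 0.05 and 80% power. The assumed proportions are blacked out. The SAP concludes that "a sample size of 24 study subjects is determined to be sufficient to provide appropriate sample population for statistical analysis" and, in the same sentence, that "the results of this retrospective study can be considered statistically and clinically meaningful and generalizable to the broader intended population". Protocol section 11 has the same sentence. A shorter statement, that 24 is enough for the results to generalize, opens Protocol section 11 and recurs in the Target Number of Subjects per Site row of SAP Table 6.

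On safety, SAP Table 5 sets no hypothesis because "formal safety evaluation is not required for this non-significant risk (NSR) retrospective study", and it confines significance evaluation to the primary efficacy variable. The Adverse Events section says that "incidence rates and percentages of adverse events will be calculated with respect to each of number of subjects and number of treatment administrations". The Summary of Study Data section gives categorical measures as frequencies and percentages. Confidence intervals are mentioned only in the interim-analysis table, in a row marked not applicable.

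The documents differ on who is counted. Protocol section 11 evaluates safety in a separate safety population. SAP Table 7 makes the per protocol population the only one. The Subject Disposition section describes that population as subjects who had two or three treatments and completed both follow-ups.

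**The concern.** A power calculation for one proportion says something about that proportion only. It gives no assurance about the precision of an adverse-event rate. Nor can a sample size by itself make any result generalizable: that depends on how subjects were selected, and here they are drawn from a completed source study and filtered by further exclusions, including one on photograph comparability.

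What is at stake is how an adverse-event table is read. A row showing 0% with no interval, beside a statement that the results are meaningful and generalizable, invites the reader to treat 0% as well established. Protocol section 11 foresees bulletins, a white paper and publications, where that reading could spread. With about 24 subjects, an event that affects a few percent of patients could easily go unseen.

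**Working it through.** **The plan's own figure.** The sample size of 24 can be neither confirmed nor refuted, because the assumed proportions are blacked out and the sidedness of alpha is not stated. It is attainable. With one-sided alpha 0.05, a null rate of 0.55 and a true rate of 0.80, 24 is the smallest N that reaches 80% power (success at 18 or more of 24, actual alpha 0.036, power 81.1%). If the null rate were instead the 70% of SAP Table 5, the rule at 24 would be 21 or more (actual alpha 0.042), with power 78.6% at a true rate of 0.90 and 97.0% at 0.95. Whichever values were used, the calculation concerns responders, so the redaction does not affect this point.

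**Inputs for safety precision.** N = 24 is from SAP Table 6. The subject-level count, with each subject counted once, is from the SAP Adverse Events section. The number of events is not in the documents; zero is assumed as the most favourable case, and one to three are shown as a range. Because 24 is a minimum and all eligible source-study subjects are to be analysed, N = 20 and N = 30 are also shown.

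**Zero events.** The exact (Clopper-Pearson) two-sided 95% upper limit is 1 − 0.025^(1/N). The one-sided 95% limit is 1 − 0.05^(1/N).

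| N | Two-sided upper limit | One-sided upper limit |
|---|---|---|
| 20 | 1 − 0.025^(1/20) = 16.8% | 13.9% |
| 24 | 1 − 0.025^(1/24) = 14.2% | 1 − 0.05^(1/24) = 11.7% |
| 30 | 1 − 0.025^(1/30) = 11.6% | 9.5% |

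**One to three events in 24.** The exact two-sided 95% limits, from beta quantiles, are:

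- 1/24: 0.1% to 21.1%
- 2/24: 1.0% to 27.0%
- 3/24: 2.7% to 32.4%

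**Chance of seeing no case in 24 subjects.** With true subject-level risk p this is (1 − p)^24:

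- p = 1%: 0.99^24 = 79%
- p = 2%: 0.98^24 = 62%
- p = 5%: 0.95^24 = 29%

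An absence of events among 24 subjects is therefore compatible with risks that a bare 0% would hide.

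**The case against.** The strongest reply is that the plan already limits its inference. Safety is openly descriptive, significance evaluation is confined to the primary efficacy variable, and there is no safety hypothesis, threshold or success rule. The generalizability sentence in Table 6 begins as a conclusion from the responder power calculation, so its reference to results may mean only the responder result. This stands to a large extent. A reader might infer that the plan declares 24 subjects adequate to establish safety, or that it contains a hidden safety conclusion. The documents support neither. But the sentence carries no limit, the shorter statements at the start of Protocol section 11 and in the Target Number row are just as broad, and the objective includes safety. Having no hypothesis test also gives no reason to omit precision, since an interval can be purely descriptive.

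A second reply is that 14.2% depends on exactly 24 subjects, zero events and a two-sided 95% convention. That is correct, and the figure should be quoted only with those conditions. The range above shows that the conclusion does not turn on them.

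A third matter is the per-treatment denominator. Treatments within one person are not independent, and a reader might infer that the SAP claims false precision by counting them. Treated as independent, 0/48 and 0/72 treatments (two or three for each of 24 subjects) would give upper limits of 7.4% and 5.0%. The SAP proposes no such interval, however, and a per-treatment percentage reported beside the subject-level one is not a claim of precision.

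Finally, parts of the documents are not visible, including the Protocol's population definitions. The absence of a safety interval is therefore a statement about the visible text.

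**Conclusion.** The point holds as one about wording and reporting. The sample size rests only on the responder-rate comparison, and four statements across the two documents claim more than that supports. Safety is part of the objective, yet the visible SAP gives adverse-event percentages with no measure of precision. With 24 subjects and zero events, the data could not exclude a rate of about 14% (two-sided 95%; 11.7% one-sided); the two-sided limit is 16.8% at 20 subjects and 11.6% at 30. These figures assume independent subjects and an observed count of zero.

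The point does not show that 24 is wrong for the primary endpoint, or that the planned percentages are incorrect.

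The safety denominator is also unsettled between the documents. If only per protocol subjects count, those who stopped early, including any who stopped because of an event, drop out. No interval corrects for that.

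**What to change.** 1. **Settle the denominator first.** Reconcile the safety population of Protocol section 11 with the per protocol-only rule of SAP Table 7 and the Subject Disposition section, and state which subjects form N for adverse events.
2. **Narrow the statements.** In both places in Protocol section 11 and both rows of SAP Table 6, limit the statement to the primary responder rate and drop the claim that sample size makes the results generalizable. Possible wording: *The sample size of 24 was chosen for the power of the primary responder-rate comparison. It was not chosen to give a set precision for adverse-event rates.*
3. **Add precision.** In the SAP Adverse Events section: *Each subject-level incidence, including zero counts, is reported as n/N with an exact (Clopper-Pearson) two-sided 95% confidence interval, as a descriptive measure of precision. Per-treatment rates are descriptive and carry no interval.*

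The cost is some wording, one extra column in the adverse-event table and a more modest safety statement. No new data are needed and the sample size does not change.

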Per Protocol Population	The per protocol (PP) population as explained above will be the primary and only analysis population in this retrospective study.

Covariates and Subgroups

Multi-center Studies

- Individual center results will be pooled together to perform the final efficacy analysis.

	Name: MXP23001 Statistical Analysis Plan	
Number: 10-040-02025	Effective Date: See Agile	Revision: A

- The justification for combining of study data across test sites is based on the clinical assessment provided by Meinert (1): the clinical (source) study was conducted under a common protocol for each investigational site, the study sites were monitored for protocol compliance, and the same data gathering instruments and methods were used at every site.
- Justification of the plausibility of combining of study data across test sites will be conducted through Fischer's Exact Test to evaluate for homogeneity of Responder Rates (study Primary Efficacy Outcome assessment) between test sites.

This study has not been explicitly designed with enough power to detect center effects. Therefore, treatment-by-test site interactions will be analyzed descriptively only through tables and charts, using N, mean, standard deviation, and minimum-maximum values. **Missing Data**

As by virtue of the study selection criteria, qualifying subjects will have had valid required measures recorded at baseline and endpoint assessments for the current study, including evaluable digital photographs, handling of missing data is not applicable.

Interim Analyses and Data Monitoring (as applicable)

N/A

Table 8

Interim Analysis Plan	
Purpose of Interim Analysis	 N/A, Explain rationale: There is no uncertainty as to the study design, treatment parameters, outcome variables, study endpoints, or endpoint analyses.
Planned Schedule of Interim Analyses	 N/A, Explain rationale: No interim analysis is planned for this study.
Scope of Adaptations	 N/A, Explain rationale: No interim analysis is planned for this study.
Stopping Rules	 N/A, Explain rationale: No interim analysis is planned for this study.
Analysis Methods to Minimize Bias	 N/A, Explain rationale: No interim analysis is planned for this study.

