Adjustment of Confidence Intervals and p-values	 N/A, Explain rationale: No interim analysis is planned for this study.
Interim Analysis for Sample Size Adjustment	 N/A, Explain rationale: No interim analysis is planned for this study.
Practical Measures to Minimize Bias	 N/A, Explain rationale: No interim analysis is planned for this study.
Documentation of Interim Analyses	 N/A, Explain rationale: No interim analysis is planned for this study.

SUMMARY OF STUDY DATA

- All continuous variables will be summarized in tables using the following descriptive statistics: n, mean, standard deviation, maximum and minimum.

	Name: MXP23001 Statistical Analysis Plan	
Number: 10-040-02025	Effective Date: See Agile	Revision: A

- All categorical measures will be summarized in tables and/or charts as frequencies and/or percentages of observed levels.
- Summary tables will be structured with a column for the treatment and rows for the variables.
- Primary efficacy outcome data will additionally be listed by subject, and sorted by site, and when appropriate by visit within subject.

Subject Disposition

The following variables from the CRF will be used to establish subject disposition with respect to those selected from the source study per the current retrospective study selection criteria:

- Number received two or three study treatments and completed 1-month and 3-month follow-ups = Per Protocol population

Determination of population membership and population size per treatment group is not applicable as this study is a single arm design with no sham or control arm.

Derived Variables

The primary endpoint of blinded evaluator before/after photo determination will be derived from the photographs that are source documents recorded at the respective evaluation timepoints during the study from which the current retrospective study data will be drawn.

Protocol Deviations

There are no significant protocol deviations in the current retrospective study that could impact the study primary outcomes analysis. With respect to the source study, given that the subject selection criteria will result in a per protocol analysis population only for the current study data, there will be no major protocol deviations that could impact that study's primary outcomes analysis.

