Any additional protocol deviations that occurred in the source study that are relevant to the current study will be listed and explored as applicable. There is no criteria for reporting of any protocol deviation that may potentially cause harm to a subject to the IRB as the source study is complete and any such reporting requirements have already been satisfied.

Demographic and Baseline Variables

The demographic or baseline variables that will be recorded in this clinical study are age, gender, race/ethnicity, and Fitzpatrick Skin Type (I through VI).

Depending on the final enrollment sample, age may be transformed into category, within the inclusion range of 18-75 years.

Demographic/baseline variables will also be summarized by test site.

Concurrent Illnesses and Medical Conditions

Subject medical history and concomitant medication use will not be specifically evaluated in this retrospective study. It is a condition of eligibility in this retrospective study that qualified subjects met the eligibility criteria under FUFT2002 and were enrolled into FUFT2002 study at which time any medical history and concomitant medication use that would be pertinent inclusion/exclusion criteria for the current retrospective study would have been satisfied. Given that the current study is retrospective, medical history and concomitant medication use will not be tracked throughout the course of the study, and as such, no coding system needs to be implemented.

Treatment Compliance

As this study is a retrospective study, assessment of treatment compliance is not applicable.

	Name: MXP23001 Statistical Analysis Plan	
Number: 10-040-02025	Effective Date: See Agile	Revision: A

EFFICACY ANALYSES

The primary efficacy variable will be listed by subject. Primary data will be summarized across the pooled subject group. N, Mean, Standard Deviation, Minimum and Maximum will summarize continuous efficacy variables, whereas number and percent will summarize categorical efficacy variables, including responder rate variables.

Responder rate variables will be assessed against a predetermined criterion.

Categorical efficacy measures will be evaluated descriptively within evaluations and for change across evaluations.

Primary Efficacy Analysis

Primary Efficacy Endpoint is pre-defined as the percentage correct before and after treatment photograph determinations made by blinded evaluators based on perception of facial wrinkles.

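### Does the low-powered Fisher test offered in support of pooling sites, and the mislabelled site interaction beside it, call for a change to the SAP?

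*SAP*

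**What the plan says.** The SAP's Multi-center Studies section makes four statements.

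- Pooling is stated without condition: "Individual center results will be pooled together to perform the final efficacy analysis".
- The first ground is clinical: one protocol at every site, monitoring for compliance, and the same instruments and methods.
- A further ground follows: "Justification of the plausibility of combining of study data across test sites will be conducted through" a Fisher exact test of whether responder rates are homogeneous between sites. No significance level, reading rule or consequence is attached to it.
- The next paragraph says: "This study has not been explicitly designed with enough power to detect center effects". For that reason, "treatment-by-test site interactions will be analyzed descriptively only through tables and charts, using N, mean, standard deviation, and minimum-maximum values".

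Other sections bear on this. Under Subject Disposition, the SAP says "this study is a single arm design with no sham or control arm". Under Summary of Study Data, "Primary efficacy outcome data will additionally be listed by subject, and sorted by site". Under Efficacy Analyses, "number and percent will summarize categorical efficacy variables, including responder rate variables". In Table 6, the row for the target number per site gives only the overall total: "A sample size of 24 study subjects has been determined sufficient to provide an appropriate sample population". The protocol synopsis says that the source study enrolled at up to five sites.

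**The concern.** The test is given a task it cannot do. Only a non-significant result could count in favour of pooling, and failing to reject equal rates does not show that they are equal. The SAP's own next paragraph concedes the lack of power. A report could therefore state that the sites were shown to be homogeneous on the strength of a p-value that would probably have been non-significant even with substantial differences.

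The interaction wording is also wrong for this design. A treatment-by-site interaction is a difference between sites in a treatment contrast, and a single arm has no such contrast. Mean, standard deviation and range are awkward summaries of a yes/no responder status, for which the SAP elsewhere asks for number and percent.

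What would be at stake is how far the pooled rate can be generalised. A single strong site might carry the result past 70% without the Fisher test signalling it.

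**Working it through.** **Inputs.** Total N = 24 (SAP Table 6, where it is the minimum size). Up to five sites (protocol synopsis). Success at a pooled responder rate of 70% (SAP, Primary Efficacy Analysis). The study's significance level is 0.05 (SAP Table 6); no separate level is given for the site test, so 0.05 is assumed for it. The number of contributing sites, the split of subjects and the true site rates are not in the documents; those below are assumptions. The SAP gives no figure for the site test, so there is none to reproduce. The assumptions behind the 24 are blacked out.

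**Step 1: one table by hand.** Take two sites with 11/12 and 7/12 responders (92% and 58%), 18 of 24 in total. With the margins fixed,

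P(X = 11) = C(12,11) × C(12,7) / C(24,18) = 12 × 792 / 134,596 = 0.0706

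P(X = 12) = C(12,12) × C(12,6) / C(24,18) = 924 / 134,596 = 0.0069

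The sites are equal in size, so the two-sided p = 2 × (0.0706 + 0.0069) = 0.155. A 33-point observed gap is non-significant.

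**Step 2: exact power.** For each split, list every site-by-response table, compute its Fisher (Fisher-Freeman-Halton) p-value, and add up the binomial probabilities of the tables with p ≤ 0.05.

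| Split | True site rates (%) | Power |
|---|---|---|
| 5/5/5/5/4 | 90, 80, 70, 60, 50 | 13.7% |
| 6/6/6/6 | 90, 80, 60, 50 | 18.5% |
| 8/8/8 | 90, 70, 50 | 21.7% |
| 10/6/4/2/2 | 90, 80, 70, 60, 50 | 30.3% |
| 12/12 | 90, 50 | 42.5% |
| 5/5/5/5/4 | 90, 90, 90, 40, 40 | 49.1% |
| 8/8/8 | 90, 90, 40 | 50.9% |
| 12/12 | 90, 40 | 63.9% |
| 12/12 | 90, 30 | 82.6% |
| 20/20 (N = 40) | 90, 50 | 74.2% |
| 8/8/8/8/8 (N = 40) | 90, 80, 70, 60, 50 | 26.2% |

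A 40-point spread is usually missed at N = 24. Larger gaps, or a larger N in two sites, are often detected. The power criticism therefore depends on a split and an N that are not known. The logical point, that non-significance is not evidence of homogeneity, holds at any N.

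**Step 3: does the test feed into the decision?** Pooling is stated first and without condition. The primary analysis compares the pooled rate with 70%; at N = 24 that means 17 responders (17/24 = 70.8%; 16/24 = 66.7%). No rule makes this depend on the Fisher p-value or on a site summary. Rewording either item leaves the count of 17 and the decision unchanged.

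**Step 4: are site rates already available?** For a responder coded 0/1, the mean is the responder rate, so N and mean by site amount to n/N. The Fisher test itself requires the site-by-responder table, and the subject listing is sorted by site. The Efficacy Analyses section gives the rule for categorical variables, number and percent, and can be read together with the Multi-center Studies section, which does not say which variables its statistics apply to.

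**Step 5: would a leave-one-site-out table add information?** Use the 5/5/5/5/4 split.

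- Rates 90/80/70/60/50%: P(pooled rate ≥ 70%) = 0.603; P(pooled ≥ 70% and below 70% without some one site) = 0.342. Ratio: 0.342 / 0.603 = 57%.
- All sites at 70%: the corresponding values are 0.565 and 0.284. Ratio: 0.284 / 0.565 = 50%.

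In this scenario, the table would raise an alarm in half of the successful trials with identical sites, and in only slightly more when rates differ by 40 points.

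**The case for a change.** The strongest case for a change is that the SAP claims an inference its own next sentence undercuts, and names an effect its design cannot have, while the repair is two sentences and a small table. A result such as 5/5, 5/5, 3/5, 2/5, 2/4 pools to 17/24 = 70.8% with Fisher p = 0.11, yet is 12/19 = 63.2% without either of the sites at 5/5. Table 6 of the SAP says the results will generalise to the intended population, so dependence on one site is a fair question.

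The first part stands: the sentence about justification is poorly reasoned, and the interaction is undefined. But the limitation is disclosed directly after the test, the clinical ground for pooling is enough by itself, and a competent analyst can only produce responder counts and percentages by site. The example is arithmetically correct, but step 5 shows that such patterns are almost as common when sites are alike, so a table of them would not answer the question. It is also too strong to say that a non-significant test is likely whenever sites differ widely: with 12 subjects in each of two sites, 90% against 30% is detected about 83% of the time.

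**Conclusion.** The drafting is imprecise, but no change follows, because nothing would be gained in the result. Under the assumed splits of 24 subjects, the Fisher test has about 14% to 42% power for a 90%-to-50% spread in site rates, and more for larger gaps. A non-significant result should therefore not be reported as proof that sites agree; the SAP's own statement on power already points the reader that way. The interaction wording is a slip for a description of site effects, which analysts will supply as n/N (%) under the SAP's general rule for responder rates. Pooling and the 70% decision depend on neither item. The power figures rest on N = 24, a level of 0.05 and assumed splits and rates; the conclusion that the primary result is unaffected rests on the SAP's wording alone.
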